### 6.6.3 Secondary endpoints

Handling of missing data for the change from baseline to week 6 in exercise capacity as measured by the distance walked in 6 minutes will be analogous to the primary endpoint, see [Table 6.6.3:1](#)

Table 6.6.3: 1 Imputation rules for missing exercise capacity at week 6

	Category	Ranking	Case description	Imputed change from baseline in 6MWT for described case (in m)*
1	Missing data on 6MWT at week 6 and no clinical event: Patients with missing 6MWT at week 6 and no event as in category 2 or 3	Ranked above patients who died or patients with a clinical event, but below patients with available measurement at week 6.	No information of post-baseline 6MWT distance and no clinical event	-354
2	Missing data and clinical event (except death). A clinical event is defined as ongoing SAE or AE leading to treatment discontinuation and patient is alive at week 6	Ranked above patients who died, but below patients with missing data and no clinical event.	Patient has ongoing SAE or AE leading to treatment discontinuation, no information of week 6 6MWT distance and patient alive at week 6.	-356
3	Patient died before the measurement of 6MWT at week 6 was conducted.	Ranked by time to death from randomisation	Patient died y days after randomisation	$-358+y/1000$

#### 6.6.4 Longitudinal Analyses

There will be different methods of analysing continuous longitudinal data.

##### Observed case on-treatment (OC-OT):

Only the available data that were observed while patients were on study medication (defined as time from first drug intake until last permanent treatment stop date plus the endpoint specific follow-up time (as defined in [Table 6.1:2](#))) are considered.

Measurements are assigned to planned weeks according to [Table 6.7: 2](#)

Imputed records are not included

##### Observed case including data after treatment discontinuation (OC-AD):

All available data are considered, including values obtained on treatment or post-treatment. Imputed records are not included.

Measurements are assigned to planned weeks according to [Table 6.7: 1](#) and [Table 6.7: 2](#)

Worst case imputation (WCI):

All available data as described for OC-AD and additionally including worst case imputation as described in [Sections 6.6.1 – 6.6.3](#). This imputation will only be considered in non-parametric analyses.

### **6.6.5 Safety Analyses**

There will be no imputation of data for safety analyses.

### **6.6.6 Missing dates**

Adverse event data

Missing or partial date information for AEs will be replaced according to general Boehringer Ingelheim (BI) rules described in the BI guidance for handling of missing and incomplete AE dates (2).

Partial onset dates from clinical event committee (CEC):

In the unlikely case that only the year is documented, the day and month will be imputed as 01 Jan unless the subsequently derived date is before randomisation; in this case the date of randomisation will be used as start date.

If year and month is present the day will be imputed as first of the month unless the subsequently derived date is before randomisation; in this case the date of randomisation will be used.

Death date

For patients with a record of death captured on the electronic case report form (eCRF) with missing or only partial death date from all available sources, the death date will be derived as the latest date of any dates as of: event onset and end dates from either the AE page, or CEC adjudicated onset dates, by using also imputed AE dates, range or of possible days based on partial death date and date of last contact.

Missing information on the date of first administration of trial drug

If the date of first drug administration is missing but the patient was randomised, the date of the first drug administration will be set to the date of randomisation. If the date of first administration is partially missing with the month and year present, the day will be set to the date of randomisation if randomisation was in the same month. If randomisation was in the month prior to the first drug administration the missing day will be imputed as the first day of the month.

Missing date of last contact date:

If the date is partially or completely missing, use the minimum of the following dates:

- the date of Informed Consent (IC) withdrawal (if applicable)
- date of death
- If the patient did not die and did not withdraw consent, the latest of:
  - visit end dates,
  - drug administration dates,
  - last drug stop date,
  - last assessment date (ECG date, date of KCCQ, date of CHQ)
  - AE onset and AE end dates
- (in case for partially missing date) Last day of the year/month given as partial date

In case of a partially missing date, if the imputed date is before the first day of the month/year given as partial date, the first day of the month/year will be used.

All other cases need to be assessed by the trial team on an individual patient basis, using the above points as guidance.

#### Missing information on the date of trial medication stop

If the date is partially or completely missing, use the minimum of the following dates:

- End of treatment visit date (if available)
- Date of death (if applicable)
- Trial completion (last contact date)
- Longest treatment duration (assuming 1 tablet/day)
- (in case for partially missing date) Last day of the year/month given as partial date

In case of a partially missing date, if the imputed date is before the first day of the month/year given as partial date, the first day of the month/year will be used.

All other cases need to be assessed by the trial team on an individual basis, using the points above as guidance.

#### Missing information on concomitant therapy dates

For incomplete date information the midpoint of the possible interval will be used. If only the year is present the day and month will be imputed as 01 July, if year and month is present the day will be imputed as 15. If the year is missing, the date will be considered missing.

If this leads to contradictions for the start or end date of a concomitant therapy (e.g. imputed end date before documented start date) a partial end date will be imputed as the end of the interval or a partial start date will be imputed as the start of the interval in the database to resolve this contradiction.

All other cases or conflicting cases resulting from these imputation rules need to be assessed by the trial team on an individual basis.

## 6.7 BASELINE, TIME WINDOWS AND CALCULATED VISITS

For serum creatinine and values based upon this measurement such as eGFR, baseline will be defined as the mean of all available measurements from the screening visit until start of randomised trial medication. For all other endpoints, baseline will be defined as the last available measurement before start of randomised trial medication.

Since the protocol specifies that all measurements are taken at visit 2 before any intake of trial medication, all measurements at the first day of drug intake are assumed to qualify as baseline measurements. For laboratory values, clock time is recorded. If a lab measurement is done after treatment start, this will not qualify as baseline measurements, except in case of HbA1c, which is considered to be a stable measurement and qualifies for baseline on the whole day of first treatment intake.

For randomised patients without any treatment intake: For serum creatinine and values based upon this measurement such as eGFR, baseline will be defined as the mean of all available measurements from the screening visit until and including the day of randomisation. For all other endpoints, baseline will be defined as the last available measurement before or on the day of randomisation.

Medication taken at baseline is any medication with start date continued or before date of first study medication intake (randomisation for patients not treated) and end date continued or on or after date of first medication intake (randomisation for patients not treated).

Measurements taken after the first intake of randomised trial medication will be considered on-treatment values if they have been obtained up to end of the parameter specific follow-up period as defined in [Table 6.7: 1](#) below and will be assigned to the randomised study drug for efficacy and safety analyses.

Measurements taken after the end of the endpoint specific follow-up period after the last intake of study drug will be considered post-treatment values.

On-treatment (for OC-OT analysis) or all post-randomisation (for OC-AD analysis) efficacy and safety measurements will be assigned to visits based on time windows around the planned visit dates. These time windows are defined based on the planned number of days after the date of first administration of study drug.

The time window for the first visit after randomisation starts on the day after the first intake of study drug. For the primary analysis of the primary endpoint and the key secondary endpoints, the start of the time window of week 12 assessment will follow the protocol defined time window (refer to [Table 6.7: 1](#) for details). For all sensitivity analyses and all other endpoints the midpoint between two on-treatment visits defines the end of a time window, with the midpoint being included in the time window of the preceding visit ([Table 6.7: 2](#)).

Table 6.7: 1 Time windows for primary analysis of primary and key secondary endpoints and Sensitivity analyses using Wilcoxon model

Visit number	Visit label	Planned days	Time window (days after baseline)	
			Start	End
2	Baseline 	1	NA	+1
3	Week 6	43	+2	+77 
4	Week 12	85	+78	NA 

 Only values taken prior or on the day of treatment start with randomised study drug can be considered baseline values. To be conservative, all data on the day of treatment start will be assumed to be before treatment start for 6MWT and PROs. Time windows will be used for assignment of measurements to scheduled visits.

 For patients with no value in the visit 4 window (visit 3 window respectively), determination of imputation categories will be: deaths before day 92 (day 77 respectively) will be considered for imputation category 3; value for patients with clinical event overlapping at least partially with the time window day 78 to day 92 (day 2 to day 77 respectively) will be imputed according to imputation category 2.

Table 6.7: 2 Time windows for measurements except primary analysis of primary and key secondary endpoints [OC-OT]

Visit number	Visit label	Planned days	Time window (days after baseline)	
			Start	End
Endpoints assessed at each on-site visit (e.g. creatinine / eGFR)				
2	Baseline 	1	NA	+1
3	Week 6	43	+2	+64
4	Week 12	85	+65	Trt stop + x* days
FU	FU	Trt stop + 7 days	Trt stop + x* + 1 day	NA
Endpoints that are not assessed on visit 3 (e.g. weight)				
2	Baseline 	1	NA	+1
4	Week 12	85	+2	Trt stop+ x* days
FU	FU	Trt stop + 7 days	Trt stop + x* + 1 day	NA

 Only values taken prior to the start of treatment with randomised study drug can be considered baseline values. Time windows will be used for assignment of measurements to scheduled visits.

\* see [Table 6.1: 2](#)

Table 6.7: 3 Time windows for measurements except primary analysis of primary and key secondary endpoints [OC-AD]

Visit number	Visit label	Planned days	Time window (days after baseline)	
			Start	End
Endpoints assessed at each on-site visit (e.g. creatinine / eGFR)				
2	Baseline 	1	NA	+1
3	Week 6	43	+2	+64
4	Week 12	85	+65	NA
Endpoints that are not assessed on visit 3 (e.g. weight)				
2	Baseline 	1	NA	+1
4	Week 12	85	+2	NA

 Only values taken prior to the start of treatment with randomised study drug can be considered baseline values. Time windows will be used for assignment of measurements to scheduled visits.

For examinations that are not planned at every on-treatment visit, the time windows will be defined according to the same algorithm, based on the midpoint between the planned visit day of such an examination. Examples for eGFR and weight can be found in [Table 6.7: 2](#) for OC-OT analyses and in [Table 6.7: 3](#) for OC-AD analyses.

Only one observation per time window will be selected for analysis at an on-treatment visit – the value will be selected which is closest to the protocol planned visit day.

For the primary endpoint (6MWT) and any measurement related to the 6MWT assessment the longest walking distance for each day will be used for the analysis for that day.

If there are two measurements which have the same time difference in days to the planned day, or if there are two measurements on the same day (endpoints not related to the 6MWT), the first value will be used.

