### **6.2.3 Follow up period and trial completion**

A follow up visit will be performed 7 days (+7 day window) after the last dose of trial medication. The assessments to be performed at the follow-up visit are indicated in the Flowchart. The follow-up visit marks the completion of the study for the individual patient.

See [Section 3.3.4.1](#) for procedures to be followed in case a patient prematurely discontinues trial treatment.

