## 7.6 FURTHER ENDPOINTS

All further endpoints will take into account all data, regardless of whether the patient was on treatment or not, and without imputation of missing values (OC-AD).

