### **7.6.3 Continuous endpoints**

Further continuous endpoints are generally analysed in a mixed model with repeated measures (MMRM), including visit-by-treatment interaction and baseline-by-visit interaction. An unstructured covariance structure will be used to model the within-patient errors. The MMRM analyses will also be shown graphically.

Descriptive statistics will be calculated for the value at visit and change from baseline.

- Change from baseline in KCCQ overall summary score, CSS, and individual domains at Week 6 and week 12
- Change from baseline in CHQ individual domains at week 6 and week 12
- Change from baseline in SBP at Week 6 and week 12
- Change from baseline in DBP at Week 6 and week 12

The following endpoint is assessed as part of the main analysis or sensitivity analysis of the corresponding secondary endpoint:

- Change from baseline in KCCQ TSS at Week 6
- Change from baseline in CHQ-SAS dyspnea at Week 6
- Change from baseline in Clinical Congestion Score at week 6.
- Change from baseline in NT-proBNP at week 6.

Since bodyweight is only measured at baseline and week 12, an ANCOVA model will be presented including baseline weight as a covariate.

Descriptive statistics are planned for:

- Change from baseline to week 6 and week 12 in patient-rated assessment of dyspnea and fatigue by the Borg scale as part of the 6MWT

For the following parameters measured at the follow-up visit, additionally descriptive statistics at baseline, last value on treatment and follow-up will be presented for patients with valid measurements at all three timepoints. .

- SBP
- DBP

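### For SBP and DBP, the open-ended OC-AD week 12 window can replace an on-drug Visit 4 value taken 4 to 7 days early with an off-drug follow-up value.

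*SAP*

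**What the plan says.** **Endpoint and data.** SAP 4.1 adds blood pressure to the planned analyses. SAP 7.6.3 lists "Change from baseline in SBP at Week 6 and week 12", and the same for DBP, among the endpoints analysed by MMRM. SAP 7.6 sets the data handling: "All further endpoints will take into account all data, regardless of whether the patient was on treatment or not", without imputation, which the SAP labels OC-AD.

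**Window.** SAP 6.7 says that "all post-randomisation (for OC-AD analysis) efficacy and safety measurements will be assigned to visits based on time windows around the planned visit dates". Table 6.7: 3, whose title marks it as the OC-AD table, gives the week 12 row as "4 Week 12 85 +65 NA": planned day 85, start day 65, no end. It has no follow-up row. Table 6.7: 2, the OC-OT table, closes week 12 at treatment stop plus x days and gives follow-up its own row.

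**Selection.** One observation per window is kept: "the value will be selected which is closest to the protocol planned visit day". The tie rule covers two cases. The relevant one reads "If there are two measurements which have the same time difference in days to the planned day", and the first value is then used.

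**Visits.** The protocol flow chart allows Visit 4 on day 85 ± 7 and schedules vital signs at the follow-up visit. Protocol 4.1.4 ends treatment on the day of Visit 4. Protocol 6.2.3 states: "A follow up visit will be performed 7 days (+7 day window) after the last dose of trial medication".

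**Conflicting references.** SAP 6.6.4 assigns OC-AD measurements to Tables 6.7: 1 and 6.7: 2. The SAP 6.7 text before Table 6.7: 1 also cites Table 6.7: 2 for all other endpoints. The title of Table 6.7: 3 and the text after it assign OC-AD to Table 6.7: 3.

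**The concern.** The week 12 window for OC-AD contains two blood pressure readings for an ordinary completer: one at Visit 4 on drug, and one at the follow-up visit off drug. Distance from day 85 alone decides which is called week 12. If Visit 4 was held early enough, the follow-up reading can be the nearer one. The Visit 4 reading is then discarded, although it was taken inside the protocol's own visit window.

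The SAP elsewhere treats follow-up as a separate time point. Table 6.1: 2 counts blood pressure as on-treatment only up to 1 day after the last intake. SAP 7.6.3 plans a descriptive SBP and DBP table with baseline, last on-treatment value and follow-up side by side. As written, the same reading could appear as follow-up in that table and as week 12 in the MMRM.

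At stake is the meaning of the week 12 SBP and DBP differences. If part of the drug effect on blood pressure has gone by the follow-up visit, the affected patients pull the estimated difference toward zero. Who is affected depends on appointment dates, not on discontinuation.

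**Working it through.** **Inputs**
- Planned days for weeks 6 and 12: 43 and 85 (SAP Table 6.7: 3).
- Permitted Visit 4 days: v = 78 to 92 (85 ± 7, protocol flow chart).
- Last dose: the day of Visit 4 (Protocol 4.1.4).
- Follow-up day: f = v + 7 to v + 14 (Protocol 6.2.3).
- On-treatment carry-over for blood pressure: x = 1 day (SAP Table 6.1: 2).

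**Step 1: reproduce the window boundary.** The SAP puts the midpoint between two visits into the earlier window. (43 + 85) / 2 = 64, so week 6 ends on day 64 and week 12 starts on day 65. This agrees with Table 6.7: 3.

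**Step 2: apply the selection rule.** Both v and f are at least 78, so both lie in the week 12 window. Follow-up is selected when |f − 85| < |v − 85|. A tie goes to the earlier value, Visit 4.

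| Visit 4 day | Distance from 85 | Follow-up days that are selected | Count (of 8) |
|---|---|---|---|
| 78 | 7 | 85 to 91 | 7 |
| 79 | 6 | 86 to 90 | 5 |
| 80 | 5 | 87 to 89 | 3 |
| 81 | 4 | 88 | 1 |
| 82 to 84 | 3 to 1 | none (earliest follow-up, days 89 to 91, is 4 to 6 days away) | 0 |
| 85 to 92 | 0 to 7 | none (follow-up is always further away) | 0 |

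There are 15 × 8 = 120 compliant pairs, and 7 + 5 + 3 + 1 = 16 select follow-up.

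Example: Visit 4 on day 78 is 7 days from day 85. Follow-up on day 85 is 0 days away and is used, although the patient has then been off drug for 7 days.

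**Step 3: effect of holding follow-up on the original schedule.** Protocol 6.1 asks that later visits keep their original dates when a visit is moved. The original follow-up date is 85 + 7 = 92. With Visit 4 on days 78 to 81, follow-up on day 92 is 14 to 11 days after the last dose, so still permitted. It is 7 days from day 85, against 7 to 4 for Visit 4. The tie at day 78 goes to Visit 4, so Visit 4 is kept every time: 0 affected.

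**Step 4: sensitivity to visit dates (assumed, not in the documents).** Visit 4 dates are taken as normal around day 85, restricted to days 78 to 92, with every patient attending both visits.

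| Assumed SD of Visit 4 date | Follow-up exactly 7 days later | Follow-up uniform over 7 to 14 days |
|---|---|---|
| 2 days | 3.8% | 0.8% |
| 3 days | 11.6% | 3.9% |
| 4 days | 17.0% | 6.8% |

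**Step 5: scope.** In the flow chart, 6MWT, the PROs, Clinical Congestion Score, NT-proBNP and weight are not collected at follow-up. The eGFR MMRM, creatinine over time and heart rate over time use OC-OT (SAP 7.8.2 and 7.8.3), where follow-up has its own row. That leaves the SBP and DBP MMRM.

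**The case against.** **The cross-reference may point to the safer table.** SAP 6.6.4 sends OC-AD to Table 6.7: 2, which has a follow-up row; read that way, the swap cannot occur. This is a real conflict and belongs in the point. It is unlikely to be the intended reading: Table 6.7: 2 is labelled OC-OT and closes week 12 shortly after treatment stop, which would remove the post-treatment values that SAP 6.6.4 says OC-AD includes. The SAP needs correcting on either reading.

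**Rescheduling rule.** Protocol 6.1 would hold follow-up on day 92, and then no Visit 4 value is lost. This stands as a reason to expect fewer cases. It does not remove them, because the flow chart and Protocol 6.2.3 tie follow-up to the last dose, so follow-up on days 85 to 91 remains compliant after an early Visit 4.

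**OC-AD is meant to include off-drug data.** True. But including post-treatment data does not require discarding a completer's Visit 4 value in favour of a later one.

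**The selection rule speaks of an on-treatment visit.** That phrase names the visit being filled. It does not restrict which readings in the open-ended window are candidates.

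**Low consequence.** Also true. SBP and DBP are exploratory, the rule works the same way in both arms, and on-treatment blood pressure is separately summarised, though only descriptively.

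**Conclusion.** The point holds in a limited form. Under Table 6.7: 3 as written, the follow-up blood pressure replaces the Visit 4 value when Visit 4 is 4 to 7 days early and follow-up falls soon enough within days 85 to 91. That is 16 of 120 compliant day pairs. It is a defect in the window rule for the exploratory SBP and DBP MMRM analyses.

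Stronger conclusions that a reader might draw are not supported:
- *Every early Visit 4 is affected.* Visits 1 to 3 days early never are.
- *About 13.3% of patients are affected (16/120).* That treats all day pairs as equally likely. The documents give no distribution of visit dates. The range is 0 if follow-up stays on day 92, and 0.8% to 17.0% under the assumed dates in the working.
- *The week 12 difference shrinks by the same percentage.* That requires the effect to be fully gone at the follow-up visit. The 1-day carry-over in Table 6.1: 2 is a classification rule, and the documents give no figure for the loss of effect after 7 to 14 days.
- *The trial's main results are at risk.* Primary, key secondary and other secondary endpoints are unaffected.

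It remains worth correcting, because the rule mislabels a time point and the correction costs almost nothing.

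**What to change.** 1. In SAP 6.6.4, refer OC-AD to Table 6.7: 3. Adjust the sentence in SAP 6.7 that cites Table 6.7: 2 for all other endpoints so that it names Table 6.7: 2 for OC-OT and Table 6.7: 3 for OC-AD.
2. Add one sentence under Table 6.7: 3: for OC-AD, a value from Visit 4, or from the scheduled week 12 visit of an early discontinuer, takes precedence over any value from the follow-up visit. Say also whether a follow-up value may be used when no such value exists.
3. Identify follow-up values by visit, not by the cut-off in Table 6.7: 2. Copying that row would start follow-up at treatment stop + 1 + 1 days for blood pressure. A patient who stopped on day 50 and attended week 12 on day 85 would then be classed as follow-up from day 52, and the off-treatment week 12 value that OC-AD should keep would be lost.

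With the precedence sentence, 0 of the 120 compliant pairs lose the Visit 4 value. The cost is a short SAP edit and a small change to the visit-selection program. It needs no new data and leaves the confirmatory analyses unchanged.
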